Outcome Description: Assessed by a customized computer task, where individual reaction times will be measured in response to mental rotation of body parts. There is no a standard result, it depends on the RTs of each individual, usually from 250 ms to up 5000 ms, fastest and slowest response respectively in this kind of study.

Outcome Timeframe: From Visit 1 (before tDCS-BI) to Visit 12 after10 study sessions (after tDCS-BI)

All other measures not listed in these Endpoints are exploratory and they will be examined for change and potentially be considered a primary outcome in the final analyses.

Secondary Endpoints

The change in EEG measures is a tentative outcome measure in this pilot study. Therefore, other outcomes related to Aim 2 will be examined for change and may therefore potentially be considered a primary outcome in the final analyses.

Outcome Title: Change EEG measures after BI-tDCS but not after BI-sham-tDCS

Outcome Description: Assessed by using a 64 channel EEG system. We will evaluate absolute spectral power in the frequency range of 4–35 Hz, as we will focus our analysis on theta (4–7 Hz), alpha (8–13 Hz), low beta (13-20 Hz) and high beta (20-30 Hz).

Outcome Timeframe: From Visit 1 (before tDCS-BI or before sham-BI) to Visit 12 after 10 study sessions (after tDCS-BI or after sham tDCS-BI).

All other measures not listed in these Endpoints are exploratory and they will be examined for change and potentially be considered a primary outcome in the final analyses.

7) Data Management

The ongoing protection of data and participant privacy is a recognized responsibility all project staff having access to this information, the Principal Investigator in particular. The following procedures will be applied toward the monitoring, management, protection, and integrity of data:

1. The electronic data are stored in controlled-access workgroups on secure and backed up file servers under the control of the UM Department of Information Technology.
2. Access to these workgroups is restricted to project personnel authorized by the PI.
3. Each project member has a unique logon ID, knows only his or her password, and will have access to data specific to his/her job.
4. Electronically scanned copies of the obtained medical records necessary for the establishment of study entry criteria (e.g. SCI diagnosis, etc.) will be kept on secure and backed up file servers under the control of the UM Department of Information Technology. Hard copies will be returned to the participant or destroyed by secure means.

5. Software databases (MS Access and Excel, IBM SPSS) will not contain individually identifiable or other sensitive information. A Subject ID, that is NOT based on individually identifiable information will be assigned to each participant's data.
6. A document linking the Subject ID number to the participant's identity will be under the control of the PI and maintained separately from the raw data and scanned medical records. This link will be maintained as long as the research or applicable law requires and then destroyed by secure means.
7. Documents with names, social security numbers, or other sensitive information (e.g. informed consents, W-9 tax forms, and payment request forms) will be maintained separately from research data in locked cabinets within the controlled access offices of The Miami Project to Cure Paralysis. These documents will be maintained and securely destroyed per UM policy.
8. A UM laptop with UM IT installed encryption may be used by the PI for data analysis, however, no individually identifiable data will be located on this laptop.
9. Procedures for reporting theft or loss of sensitive data are in place and familiar to the study investigators and staff who have access to, use, or store data.

Data Analysis: Parametric or non –parametric statistic will be performed depending on data distribution.

Risks to Subjects:

Risks/discomforts associated with completion of questionnaires: Some questions may be emotionally distressful to some participants or make them uncomfortable. Participants will be instructed that they can skip any questions which they do not wish to answer.

Risks/discomforts associated with measurement of sensory function (QST): Pain thresholds will be measured for cold and hot temperatures. Each stimulus trial will start at a neutral temperature (32 °C) and will be increased (for hot pain) until the participant indicates that the stimulus has just become painful. This will result in slight discomfort for the participant. As soon as the participant tells the experimenter that the stimulus is painful, the stimulus will immediately be terminated. Cut-off temperatures are in place (50 °C for hot pain) so that no extreme temperatures will be presented. The cut-off value is well below temperatures at which any skin damage would result. The equipment used for sensory testing has been used in our laboratory for many years, without any adverse events. This equipment is also used in many other laboratories and has an excellent track record.

Risks/discomforts associated with BI: bodily illusions are commonly used research tools with no risk for participants.

Risks/discomforts associated with EEG measures: EEG records brain activity at no risk to participants. The EEG is used with the only purpose of recording, the electrodes are placed on the scalp attached to a custom cap with prepared holes. We use an EEG system with active electrodes (Biosemi Active Two 64 channels: https://www.biosemi.com/faq/skin_preparation.htm) and so high electrode impedance are tolerated, and the system can be used without the usual skin preparation (scrubbing) to lower impedance. This minimizes discomfort and eliminates risks of infection. In the case of electrodes placed around the face, it is possible that participants with very sensitive skin may experience redness, however this will be very minor and solve within minutes. We use a low impedance highly conductive saline gel (Signa gel by Parker), formulated to maximize contact between the body surface and the Active electrodes, bacteriostatic, non-irritating, and non-staining.

Risks/discomforts associated with tDCS: the current applied is very weak (2mA) and there are not observed serious adverse effects associated with tDCS. Minor side effects have included (restricted to the electrode location) mild temporary burning or tingling at the site of stimulation, headaches and tiredness (Bikson *et al.*, 2016), it is a safe procedure widely used (see (Nitsche *et al.*, 2003; Poreisz *et al.*, 2007) for more information and safety aspects of tDCS use). It should be noted that other side-effects like nausea and dizziness can happen and also that they have been illustrated to occur at nearly the same rate as sham stimulation (fake stimulation) (Brunoni *et al.*, 2011). These sensations are not painful and go away when stimulation stops. When electrodes are placed too close to the eye, participants may experience phosphenes that go away adjusting the position of electrodes. tDCS it is not a medical device and it is considered a non-significant-risk device, meaning that it is a technique without expectation of any Serious Adverse Effect (Bikson *et al.*, 2016; Fregni *et al.*, 2015). We use standard procedures, which means: no more than 2mA of intensity, not more than 40 min per session, with standard electrodes (pads) that are typically square 5 × 5 cm or 5 × 7 cm (Bikson *et al.*, 2016). It has been extensively used in human research and chronic pain (Pinto *et al.*, 2018).

Please note that there is no scientific evidence that suggests lasting injury or irreversible side-effects from tDCS, all the minor sides effects are temporary.

We will explain participants the device and the possible minor side effects and we will let them familiarizing for short time by applying a very small amount of current before to reach 2mA.

Adverse Events and Serious Adverse Events associated with electrical stimulation:

temporary skin redness, itching, and tingling. Other suggested but rare side-effects of tDCS include headache, nausea, and dizziness. These sensations go away when stimulation stops.

tDCS it is not a medical device and it is considered a non-significant-risk device, meaning

that it is a technique without expectation of any Serious Adverse Effect.

Participants will report to study team if any of these side effects will be experienced, we will keep record of any reported side effect.

If the effects are experienced as uncomfortable to participants so that the stimulation will need to be stopped, we will not consider any data collected related to those participants. Participants have the right to not continue the study, in this case new participants will be enrolled for replacement.

8) Potential Benefits to Subjects

Participants may experience reduction in pain sensation, and will better understand their own pain and associated factors.

9) Vulnerable Populations

Vulnerable populations, i.e., children, individuals with moderate to severe cognitive impairment, prisoners of the penal system, and women who are pregnant will not be considered.

10) Setting

The study will take place at The Miami Project to Cure Paralysis, University of Miami.

11) Resources Available

[name] is the principal investigator of the Clinical Pain Research Laboratory of The Miami Project to Cure Paralysis. Her educational background is in cross-disciplinary pain research (pain physiology and pain psychology) and in the clinical management of chronic pain. She has performed human pain research for more than 26 years and in the field of spinal cord injury (SCI) for over 22 years. [name] has published 65 peer reviewed journal articles and written nine book chapters on pain and pain assessment. Her present research involves both qualitative and quantitative pain methodologies including quantitative sensory testing and MR spectroscopic brain imaging. She has adapted outcome measures used to classify and assess pain in other chronic pain populations to people with SCI and been instrumental in developing, presenting, and promoting the International SCI Pain Data Sets and the NINDS CDEs for SCI and Pain. She serves as the Chair or as a member in both National and International efforts to standardize pain outcome

measures and pain classification, and clinical guidelines related to pain. [name] has extensive interdisciplinary clinical pain research experience in persons with neurotrauma, including the use of a wide spectrum of pain outcome measurements and pain phenotyping.

[name] is a postdoc at the neurological surgery department at the University of Miami, Miller School of Medicine. She has an MSc degree in Cognitive and Experimental Psychology and her PhD is in cognitive sciences. Her research is focused on understanding brain mechanisms of sense of agency (motor control). Her expertise in experimental psychology and cognitive neuroscience makes her profile crucial for conducting this study. She has several publications on sense agency. In this study [name] will conduct all measurements as described in the procedures section. In [name] lab, [name] has been trained in pain research.

12) Prior Approvals

No prior approvals will be necessary before commencing the study

13) Recruitment Methods

Individuals will be recruited via the Miami Project volunteer database (provided monthly by the Director of Education and Outreach at the Miami Project to Cure paralysis. The Miami Project research volunteer database is a database of over 4000 potential and/or current research participants who have expressed an interest in being considered for participation in our research studies. These participants and their responses to an intake form are then screened for eligibility for our current research studies) and by word of mouth. In addition, participants will be solicited through the website of the Miami Project at the University of Miami (the Miami Project has a website and twitter page where they may post our protocols information and people can contact us:

<https://www.themiamiproject.org/participant/research-participation/current-studies/>.

Flyers about the study will be placed in the Miami area clinics, physical therapy, and rehabilitation centers serving patients with SCI and in University of Miami rehabilitation clinics. The research team will be located at the Miami Project to Cure Paralysis and available to speak with participants about the study prior to enrolment, to provide all the information needed. Potential study participants will be asked to contact the study coordinator if they are interested in participating in the study and schedule an appointment.

Remuneration: Participants will receive a \$250

\$50 after Sensory and Pain examination (QST); \$50 after the first week; \$150 at the end of the 2 weeks and completed tests.

14) Local Number of Subjects

The current study is a single site study. We identified a total sample size of 20 SCI individuals with neuropathic pain. Additional aspects of sample size determination are the type and significance level of the test employed.

15) Confidentiality

All data obtained in this study will be used solely for research purposes. Sources of research material include:

- (1) questionnaires and interviews with the participants regarding pain (paper data);
- (2) reaction times and accuracy (electronic data), as described in the Procedure section. Data will be therefore both paper and electronic.

Data will be coded for computer analysis, all participants' personal information will be kept separately by research findings (separation of identifiers and data) during storage, use, and transmission:

Personally Identifiable Information: For each participant, a folder will be created that contains confidential information. Extensive precautions are taken to insure the privacy of participants and the confidentiality of data. Specifically, participant identity is numerically coded on all pages within participant folders. All participant folders are kept in confidential lockers in our office at the Miami Project to Cure Paralysis .

The Personally Identifiable Information including *name, gender, ethnicity, and relevant medical (limited to know if they have pain and if they receive any treatment) and personal information* (such as *address, birth date, telephone number, email address and social security number*) is kept in a centralized, restricted access location.

Only personnel directly associated with the study have access to these files.

Data: For each participant, a folder will be created that contains all data. This folder serves as a permanent archive of original participant data. Research data will be entered into the computerized database using only the participant ID number, and without any identifying information that would compromise the identity and confidentiality of the participants.

All electronic data will be secured and password protected in UM servers.

All paper data and PII will be kept separated and secured in lockers in our office where only the research team will have access.

Choose the statements below that are applicable to this research:

26(a). Will the research collect protected health information or personally identifiable information from the EMR or from subjects at UHealth and/or JHS?

Yes (If checked go to 26(b))
 No (If checked, go to Section 27)

26(b). Check the box next to the correct statement below

Research Subjects will sign a HIPAA Authorization before the research will collect this data.
 Research Subjects will not sign a HIPAA Authorization for this data collection and the research is requesting a waiver of HIPAA authorization from the IRB. *(If checked, complete Section 17 below)*

26(c). How will the research store the data? *(See Section 26(e) below)*

On a University of Miami electronic device (e.g. encrypted, password-protected computer)
 On a cloud-based storage system that is approved by the University of Miami
 On the secured JHS SharePoint environment *(required for protected health information or identifiable information collected from JHS records without a waiver of authorization from an IRB.)*
 Other, specify: Click here to enter text.

26(d) Select one of the following:

The Principal Investigator (and/or Study Team members) will record (e.g. write down, abstract) data acquired in a manner that does not include any indirect or direct identifiers (listed in the instructions for Section 26 of this protocol), and the recorded data will not be linked to the individual's identity.

OR

The Principal investigator (and/or Study Team members) will record (e.g. write down, abstract) the data collected in a manner that does not include any direct identifiers (see list in the instructions for Section 26 of this protocol) of any subject. Instead, the Principal Investigator and/or Study Team members shall will assign a code (that is not derived in whole or in part from any direct or indirect identifiers of the individual) to each study subject and link the code to the study subject's identity. The link to each subject's identity and/ or other identifiable information will be maintained on a document separate from the research data.

26(e) Additional requirement for Jackson Health System Data:

This section applies to data that will be collected from JHS under a waiver of HIPAA authorization (without a signed HIPAA Authorization from the participant).

Not-applicable, no data will be acquired from JHS under a waiver of authorization.

JHS data, including Protected Health Information (PHI) and/or Personally Identifiable Information (PII), acquired from JHS for this research under a waiver of authorization shall only be stored on the secured JHS SharePoint environment made available by JHS. I and the Study Team members shall not copy or store the JHS sourced personally identifiable information (PII), including protected health information (PHI) data to any other system, including any systems maintained or provided by the University of Miami. I and the Study Team shall only copy or transfer JHS-sourced data that has been properly de-identified in accordance with all requirements contained in the HIPAA Rules by removing all of the identifiers listed in the instructions for Section 26 of this protocol.

16) Provisions to Protect the Privacy Interests of Subjects

See above 5) Data Management.

17) Consent Process

The consent process will be conducted by [name], [name], [name] and/or the PI [name]. The consent process will take place at The Miami Project to Cure Paralysis, The Christine E. Lynn Rehabilitation Center . To ensure candidates have full knowledge of all study obligations and potential risks and benefits; all candidates will read the common consent document and then have an open, two-way discussion with consenting staff to establish 1) that candidates have a full understanding of what their participation will entail, and 2) allow the candidates an opportunity to ask questions or express concerns and have them fully addressed before proceeding with the study. Participants can freely decide to participate taking as much time as needed. The research team will follow up by contacting the participant again. This process will be present throughout the study and the participant will continue to have access to both research staff and the PI to resolve any concern that may arise. The study population will be English-speaker since the investigators are English-speakers.

18) Authorization for Use and Disclosure of Protected Health Information (HIPAA)

If the research team will access patient medical records or other identifiable health information for this research, you must obtain a waiver of the requirement for written authorization from the patients to access their medical records.

Type of Request:

- Waiver of Authorization for access to medical record for subject identification/recruitment.

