BR measures: A computer task (mental rotation of body parts) will be performed **PRE** and **POST** BI-tDCS (or BI and inactive tDCS:sham). The mental rotation of body parts is assumed to activate somatosensory representations, such as the body schema. In this task participants will be instructed to perform a computer task: the mental rotation task of body parts. They will observe images of hands or feet (left and right) on a computer screen or objects (left or right oriented) in different angle orientation and they will have to judge the laterality of the image (left or right). Reaction times will be measured and defined as a difference from image onset and participant's vocal response, accuracy (correct responses) will be also evaluated.

EEG recording at rest: A 64-channel Biosemi EEG-system will be used to record cortical activity under two conditions of 5 min each: while subjects will rest with their eyes closed (EC), and while they will rest with their eyes open (EO) keeping the gaze on a fixation cross in the middle of a computer screen. These measures will be performed at baseline (**PRE**) and directly after treatment completion (BI-tDCS or BI-sham) (**POST**). Absolute spectral power will be calculated in the frequency range of 4–35 Hz, as we will focus our analysis on theta (4–7 Hz), alpha (8–13 Hz), low beta (13–20 Hz) and high beta (20–30 Hz).

Questionnaires: First they will be requested to report their height and weight to calculate body mass index (BMI). Participants will be also asked to complete 4 questionnaires: the Neuropathic Pain Symptom Inventory (NPSI), psychological general well-being index (PGWBI) questionnaire, the Beck Depression Inventory-II (BDI-II) and the Cambridge Depersonalization Scale. We will also perform a pain assessment using the Pain Basic Data Set where participants will describe their pains and provide the Patients' Global Impression of Change (PGIC):

1. The psychological general well-being index, The PGWBI is a validated Health

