tDCS: Direct current will be delivered from a battery-driven, constant current stimulator (TCT Research Version, Hong Kong) using saline-soaked surface sponge electrodes (35 cm²). The anode will be placed over P4 (EEG 10/20 system) to target the right Posterior Parietal Cortex (rPPC), and the cathode over the contralateral supraorbital area. This electrode position is chosen because rPPC has been shown to be involved in

multisensory integration, BR and localization of somatic stimuli (*Azañón et al., 2010; De Vignemont, 2007; Makin et al., 2008; Wertheim et al., 2020*). However, consistent with other tDCS studies on pain (*Soler et al., 2010*), where the site of stimulation is contralateral to the painful body-part, if participants have not bilateral pain and the painful site involves only the right side of the body, the anodal electrode will be placed on P3, the left Posterior Parietal cortex (lPPC), and be therefore contralateral to the painful body-part. A constant current of 2mA intensity will be applied for 30 min during the BI (15 min RHI plus 15 min WI). The duration of the stimulation has been chosen as used in previous works (*Mameli et al., 2014; Ouellet et al., 2015*).

In the sham session (inactive tDCS) there will be no stimulation. The procedure will be the same as the active tDCS but the machine will be turned off after 30 seconds.

tDCS it is not a medical device and it is considered a non-significant-risk device, meaning that it is a technique without expectation of any Serious Adverse Effect (*Bikson et al., 2016; Fregni et al., 2015*).

In the United States tDCS is not FDA approved. Some companies have an FDA (Food and Drug Administration) regulation status of “investigational” which limits the device to investigational use and not for medical treatment (*Fregni et al., 2015*). In the European Union, Canada, Brazil, Australia, and Singapore, specific tDCS products have been approved for treatment of various neuropsychiatric disorders. (*Fregni et al., 2015*).

Research centers worldwide are allowed to test tDCS in controlled clinical trials. A list of tDCS trials can be found here: clinicaltrials.gov

POST- Session (12)

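### The EEG endpoint leaves up to 512 values open, with no named summary, no error control and no rule for combining P3- and P4-stimulated participants

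*Combined protocol and SAP*

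**What the plan says.** Section 6 (Study Endpoints, Specific Aim #2, Secondary Endpoints) defines the outcome as "Assessed by using a 64 channel EEG system" and continues: "We will evaluate absolute spectral power in the frequency range of 4–35 Hz". It says the analysis will focus on theta, alpha, low beta and high beta. Section 4 (EEG recording at rest) says the system will "record cortical activity under two conditions of 5 min each", eyes closed and eyes open, before and after treatment.

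The outcome title is "Change EEG measures after BI-tDCS but not after BI-sham-tDCS". The paragraph on the Aim 2 primary endpoint, reaction time, says that other Aim 2 outcomes may "potentially be considered a primary outcome in the final analyses"; EEG is one of these.

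Section 4 (tDCS) puts the anode at P4 by default, citing the role of the right posterior parietal cortex in multisensory integration and body representation. If pain is on the right side only, "the anodal electrode will be placed on P3".

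The only analysis statement is one sentence in section 7 (Data Analysis): parametric or non-parametric statistics, depending on the distribution. No significance level, multiplicity rule, EEG region or averaging rule is given, and nothing says how the EEG analysis treats the side of stimulation.

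**The concern.** Three gaps act together.

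- **Many values and no chosen one.** An analyst who follows the protocol may look at any channel, band and condition, or any average of them, and report whichever changed.
- **The wording of the contrast.** A change in the active arm but not in the sham arm suggests two within-arm tests. A significant result beside a non-significant one does not show that the arms differ.
- **Two stimulation sides.** If some participants are stimulated on the left, the P4 channel lies under the anode for some and on the opposite side for others.

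At stake is the reading of Aim 2. An EEG finding could be a chance result chosen after the fact and then called primary, while a real effect near the anode could be weakened by pooling.

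**Working it through.** The documents give no number of EEG tests, significance level, effect size or standard deviation, so there is no stated figure to reproduce.

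**Inputs from the protocol:** 64 channels, 4 bands, 2 conditions, 8 participants per arm (section 4). Section 14 gives a total of 20 instead of 16, and the two must be reconciled; 10 per arm is also shown where it matters.

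**Assumed:** 5% two-sided per test; the correlations below; a P3 share f from 0 to 0.5; a local standardised effect d = 1.0.

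**Step 1, count.** 64 x 4 x 2 = 512 values. Averaged over channels, 4 x 2 = 8.

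**Step 2, false positives.** Expected number with no true effect: 512 x 0.05 = 25.6, whatever the correlation. For 8 independent values, the chance of at least one is 1 - 0.95^8 = 33.7%.

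EEG values are correlated, so trials with no effect were simulated: two arms of 8, two-sample t-tests, 3,000 runs per setting. The 64 channels were spread over a hemisphere, with correlation c + (1 - c) x exp(-distance/L), c from 0 to 0.8 and L from 0.3 to 0.7. The last column is the chance that some value among the 512 is significant within the active arm and not within the sham arm.

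| Mean channel correlation | Band / condition correlation | Any of 512 | Any of 8 averages | Active but not sham, any of 512 |
|---|---|---|---|---|
| 0.06 | 0 / 0 | 100% | 34.0% | 100% |
| 0.14 | 0.3 / 0.5 | 100% | 30.1% | 100% |
| 0.40 | 0.3 / 0.5 | 100% | 32.1% | 100% |
| 0.57 | 0.5 / 0.7 | 99.4% | 25.6% | 99.3% |
| 0.74 | 0.6 / 0.8 | 90.7% | 21.5% | 92.1% |
| 0.84 | 0.8 / 0.9 | 64.5% | 17.8% | 67.3% |

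(100% is rounded.) The average count of false positives stayed between 24.9 and 27.2, in line with 25.6.

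**Step 3, side of stimulation.** Suppose the effect is confined to the anode side and a share f of the active arm has the anode at P3. Pooled by channel name, the effect at P4 is d x (1 - f). Power is for a two-sample t-test at 5%, ignoring the extra spread that mixing adds:

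| f | Effect at P4 | Power, 8 per arm | Power, 10 per arm |
|---|---|---|---|
| 0 | 1.00 | 46% | 56% |
| 0.125 (1 of 8) | 0.88 | 37% | 46% |
| 0.25 (2 of 8) | 0.75 | 29% | 36% |
| 0.5 (4 of 8) | 0.50 | 15% | 19% |

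**Step 4, price of correcting everything.** With 8 per arm and d = 1.0, power for one pre-specified value at 5% is 46%. Under Bonferroni it is about 16% for 8 values (0.05/8 = 0.00625) and about 0.9% for 512 (0.05/512 = 0.000098). Correction alone is therefore a poor remedy; the family has to be made small first.

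**The case against.** The strongest reply is that the protocol does not say each channel will be tested. The 64 channels describe equipment, and an analyst might average them. A reader might infer that false findings are near certain; the documents do not support that. With averaging the risk is about 18% to 34%, and even channel-by-channel testing gives about 65% under very strong correlation. What remains is that 18% is still well above 5%, and the choice of summary is itself open.

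A reader might also infer that the trial does mix stimulation sides and dilute its effect. That is not established either. P3 is used only for right-only pain, the share is not given and may be zero, and pooling by channel name is not stated. The EEG rationale in section 3 (Background) concerns thalamocortical rhythms and resting oscillations and does not claim an effect limited to one side; an average over all channels would be largely insensitive to side. The loss in step 3 is conditional on all of these points.

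Mirroring channels has a weakness of its own. It treats left and right stimulation as equivalent, while section 4 justifies the default site by right-parietal function. It cannot be the only analysis.

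Finally, EEG is a tentative secondary outcome in a pilot, and the promotion clause reaches beyond EEG. This lowers the stakes, but a tentative label protects little when the same section allows outcomes to be promoted in the final analyses.

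**Conclusion.** The concern holds in conditional form. The documents establish 512 available values, no chosen summary, no error control, a one-arm-but-not-the-other contrast, a promotion clause, and a side rule with no counterpart in the analysis. At an assumed 5% per test, the chance of at least one false EEG finding is about 18% to 34% with channel averages and about 65% to nearly 100% channel by channel, given the assumed correlations. A local effect would shrink to (1 - f) if pooled by channel name, with f assumed between 0 and 0.5 and no loss at f = 0. This should be corrected, but it concerns a secondary pilot endpoint and does not touch the pain outcome.

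**What to change.** Before the data are seen, add a short EEG analysis paragraph:

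1. Name one EEG summary: for example, log power in one parietal region defined relative to the anode, in one band and one condition. Fixing the log scale also settles in advance a choice that section 7 leaves to the observed distribution.
2. Test the between-arm difference in the post-treatment value, adjusted for baseline, and reword the endpoint title as a difference in change between arms.
3. For the remaining bands, conditions and channels, use one maximum-statistic or cluster permutation test at a family-wise 5%, or label them exploratory. The permutation test relies on random allocation, which section 4 does not describe and should state if it applies.
4. Bar promotion of any EEG result to primary after the data are seen.
5. Report results with channels mirrored left to right for P3 participants in both arms, and also unmirrored. Say in advance which is the main analysis, and give the number at P3 in each arm.

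The cost is a paragraph and an analysis script. The downside is a stricter threshold and less freedom to highlight single-channel findings. Electrode placement and data collection do not change.
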